5.2 Exclusion Criteria

Refusal to participate in the study. Patients already under follow-up within our Division will not be included (only first visits). In addition, patients who undergo diagnostic or therapeutic procedures during the appointment (which is rare in first visit), such as hemorrhoid elastic ligation, will not be included in the study.

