5.1 Study population

Adult women (18 years of age or older) who present for an initial consultation at our Coloproctology Division will be studied. These patients will be randomized into two groups:

- 1- Patients undergoing proctological examination with the presence of a chaperone.
- 2- Patients undergoing proctological examination without the presence of a chaperone.

The chaperone will always be a female, and may be a nurse or nursing assistant. Her participation will be communicated to the patient, who must agree to her presence during the proctological examination. After the consultation is completed, the patient will be informed that a study is being conducted and, if she agrees to participate, she should answer a specific questionnaire regarding the physical examination that was just performed. The purpose of the study will be explained, as well as the fact that participation is voluntary, not will change her clinical management, being guaranteed the secrecy and inviolability of the information obtained.

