5.3. Primary Outcome Measure

The main outcome to be assessed will be patients' preference regarding the presence of a female chaperone during anorectal examination. It will also be assessed the degree of comfort (or embarrassment) according to the presence or not of a female chaperone during the proctological exam. This will be measured through a questionnaire compound of 6 questions (see Annexes 1 and 2). Each question will provide a isolated result (there will be no total score). The questions are the following:

1. How did you feel during the exam?
Patients will register their answer in a scale from zero (completely embarrassed) to 10 (completely comfortable)
2. What did you think of (not) having a person besides the doctor during the exam?
Patients will have 3 possible answers: bad, indifferent, good.
3. Would you rather have taken the exam in the (without) presence of another person (woman)?
There are 3 possible answers: yes, no, indifferent.
4. Do you think the (absence) presence of another person made the examination:

There are 3 possible answers: better, worse, did not change it.

5. Did you feel more (less) protected with (without) the presence of another person?

There are 3 possible answers: yes, no, indifferent.

6. In the event of a reexamination, would you want another person's presence again?

There are 3 possible answers: yes, no, indifferent.

Or: Would you again like the doctor to examine you without another person's presence?

There are 3 possible answers: yes, no, indifferent.

6. Ethical aspects

This research project follows the Normative Resolution 01/97 of the Commission for Research and Ethics in Health, as part of the Research Group and Post-graduation Program/ HCPA. There will be no change in medical investigation and management whether or not the patient decides to participate in the study. The researchers guarantee to preserve the privacy of patients whose data will be collected, to use this information solely and exclusively for the execution of this project and to publish the information obtained only anonymously.

7. Budget and sources of funding

There will be no additional cost to the HCPA with the completion of the study. The computer equipment and software required for data recording and its subsequent analysis are already available at our Division, and there is no need for new acquisitions or financing.

8. Sample size

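### Women are first asked to take part after the randomised examination, and those who refuse are excluded uncounted, so the reported levels and the between-arm comparison may be biased in either direction

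*Combined protocol and SAP*

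**What the plan says.** Section 5.1 states of eligible first-visit women: "These patients will be randomized into two groups". The groups are defined by examination with or without a chaperone. Consent to the study comes later: "After the consultation is completed, the patient will be informed that a study is being conducted and, if she agrees to participate, she should answer" what the section calls "a specific questionnaire regarding the physical examination that was just performed". That questionnaire is the only source of outcome data.

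Section 5.2 opens its exclusion criteria with "Refusal to participate in the study". Section 5.3 names preference as the main outcome and adds comfort: "It will also be assessed the degree of comfort (or embarrassment) according to the presence or not of a female chaperone". Both are self-reported.

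Section 9 gives descriptive summaries and two-group tests. It defines no analysis set, no rule for a missing outcome, no report of refusals by arm and no sensitivity analysis. Section 8 asks for 94 patients per group, with no stated allowance for refusal.

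**The concern.** In most trials, refusal is settled before randomisation and costs only generalisability. Here it comes just after the allocated examination, from a woman who already knows how embarrassed or protected she felt. Whether she answers can depend on what the questionnaire would have recorded. Because the examination differs by arm, refusal can differ by arm too. Calling it an exclusion turns a missing outcome in a randomised woman into an eligibility matter.

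Two results are exposed. The between-arm comparison would describe women willing to answer rather than the groups randomised. The level within an arm is also exposed, even if both arms refuse equally. That matters because section 4 asks whether a majority of women examined without a chaperone are satisfied or dissatisfied. With no count of refusals, a reader of the results could neither detect the bias nor put limits on it.

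**Working it through.** The plan has no refusal figure to reproduce, so this is an illustration of possible size, not an estimate.

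**Inputs.** The 31% and 14% are from section 8, where they describe women's comfort with a chaperone according to the physician's sex. They are borrowed here as assumed true dissatisfaction with the allocated condition in two arms, a true difference of 31 − 14 = 17 points. All refusal rates are assumptions.

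**Formula.** With true dissatisfaction p, refusal r among dissatisfied women and s among the others:

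observed proportion = p(1 − r) / [p(1 − r) + (1 − p)(1 − s)]

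overall refusal = pr + (1 − p)s

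**1. Selective refusal in the first arm only** (s = 5%; everyone in the second arm refuses at 5%, so 14% is still seen as 14%).
- r = 20%: 0.31 × 0.80 = 0.248; 0.69 × 0.95 = 0.6555; 0.248 / 0.9035 = 27.4%. Difference 13.4 points.
- r = 30%: 0.31 × 0.70 = 0.217; 0.217 / 0.8725 = 24.9%. Difference 10.9 points. Overall refusal in that arm is 0.31 × 0.30 + 0.69 × 0.05 = 12.75%.

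**2. The same selective refusal in both arms** (r = 30%, s = 5%). Second arm: 0.14 × 0.70 = 0.098; 0.86 × 0.95 = 0.817; 0.098 / 0.915 = 10.7%. Difference 24.9 − 10.7 = 14.2 points.

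**3. Dissatisfied women keener to answer** (r = 5%, s = 20%). First arm: 0.2945 / (0.2945 + 0.552) = 34.8%. The level is now overstated.

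**4. The majority question in section 4.** Suppose 55% are truly dissatisfied without a chaperone, with r = 30% and s = 5%. Observed: 0.385 / (0.385 + 0.4275) = 0.385 / 0.8125 = 47.4%. A true majority is seen as a minority.

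**5. Which bounds contain the truth.** Return to the r = 30% case in step 1. As shares of all women randomised, dissatisfied answerers are 21.7% in the first arm and 0.14 × 0.95 = 13.3% in the second. Refusers are 12.75% and 5%.
- All refusers counted dissatisfied: 34.45 − 18.3 = 16.2 points.
- All refusers counted satisfied: 21.7 − 13.3 = 8.4 points.
- Opposite directions: 21.7 − 18.3 = 3.4 points, and 34.45 − 13.3 = 21.2 points.

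Imputing in the same direction in both arms gives 8.4 to 16.2, which misses the true 17. Imputing in opposite directions gives 3.4 to 21.2, which contains it. For a single arm's proportion, counting refusers all one way and then all the other does bound the truth. In step 4, refusal is 0.55 × 0.30 + 0.45 × 0.05 = 18.75%, so the bounds are 38.5% and 57.25%, and they contain 55%.

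**The case against.** The strongest reply is that the documents give no refusal data at all. Refusal may be rare, and section 5.1 works to keep it so: participation is voluntary, answers are confidential and care is unaffected. A woman may also decline for want of time. Telling women only afterwards may be deliberate, so that knowledge of the study does not colour their answers. A refuser cannot be made to supply an outcome in any case.

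Much of this stands. It rules out any claim about how large the bias is, and the timing of disclosure need not change. But reassurance neither counts refusals nor handles them, and the plan does neither.

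A reader might infer that discomfort is bound to be understated, because the most upset women walk away. The documents do not support that; step 3 shows the reverse if upset women are keener to answer. A reader might also take the one-arm case as the expected loss. It is the less favourable of the two cases in steps 1 and 2: at r = 30% the loss is 6.1 points in one and 2.8 in the other. Nor does section 9 say that only returned questionnaires are analysed. It defines no analysis set, and the loss follows from sections 5.1 and 5.2.

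A woman who declines the chaperone beforehand (section 5.1: "who must agree to her presence during the proctological examination") is a separate loss, not counted here.

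**Conclusion.** The concern holds in this form. Followed as written, the plan drops women after randomisation and exposure for a reason that can depend on the outcome, and leaves no record of how many were dropped or from which arm. That rests on the sequence in sections 5.1 and 5.2, which is clear.

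Direction and size are not established. The figures rest on assumed refusal rates and on section 8's percentages used for a purpose they were not given for. They show that overall refusal of about 13% in one arm could shrink a 17-point difference to 10.9, and that other patterns shrink it less or overstate the level. A high refusal rate would not by itself prove bias or harm. This should be corrected, but it does not invalidate the design.

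**What to change.** - **Section 5.2.** Treat refusal after the examination as a missing outcome in the randomised arm, not as an eligibility exclusion.
- **Conduct.** Keep an anonymous tally against the randomisation list: arm allocated, and questionnaire answered or refused. Record no identity or clinical data. Report refusals by arm without presuming their cause. The tally must run during data collection, since refusals not noted at the visit cannot reliably be recovered.
- **Section 9, between arms.** Add a sensitivity analysis for the main preference item, naming the item and fixing in advance how its three answers are dichotomised. Impute refusers as dissatisfied in one arm and satisfied in the other, then the reverse.
- **Section 9, within arm.** For the proportion used for Hypotheses 1 and 2, give bounds with all refusers satisfied and all dissatisfied.
- **Question 1 (comfort scale).** Either impute the extremes 0 and 10 in the same opposite-direction way, or only report refusals by arm.

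The cost is a tally sheet and a few sentences in sections 5.2 and 9. The reported uncertainty will be wider, and the ethics committee must accept an anonymous count of women who refused. The questionnaire, the timing of disclosure and patient care are unchanged.

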5.3. Primary Outcome Measure

The main outcome to be assessed will be patients' preference regarding the presence of a female chaperone during anorectal examination. It will also be assessed the degree of comfort (or embarrassment) according to the presence or not of a female chaperone during the proctological exam. This will be measured through a questionnaire compound of 6 questions (see Annexes 1 and 2). Each question will provide a isolated result (there will be no total score). The questions are the following:

1. How did you feel during the exam?
Patients will register their answer in a scale from zero (completely embarrassed) to 10 (completely comfortable)
2. What did you think of (not) having a person besides the doctor during the exam?
Patients will have 3 possible answers: bad, indifferent, good.
3. Would you rather have taken the exam in the (without) presence of another person (woman)?
There are 3 possible answers: yes, no, indifferent.
4. Do you think the (absence) presence of another person made the examination:

There are 3 possible answers: better, worse, did not change it.

5. Did you feel more (less) protected with (without) the presence of another person?

There are 3 possible answers: yes, no, indifferent.

6. In the event of a reexamination, would you want another person's presence again?

There are 3 possible answers: yes, no, indifferent.

Or: Would you again like the doctor to examine you without another person's presence?

There are 3 possible answers: yes, no, indifferent.

6. Ethical aspects

This research project follows the Normative Resolution 01/97 of the Commission for Research and Ethics in Health, as part of the Research Group and Post-graduation Program/ HCPA. There will be no change in medical investigation and management whether or not the patient decides to participate in the study. The researchers guarantee to preserve the privacy of patients whose data will be collected, to use this information solely and exclusively for the execution of this project and to publish the information obtained only anonymously.

7. Budget and sources of funding

There will be no additional cost to the HCPA with the completion of the study. The computer equipment and software required for data recording and its subsequent analysis are already available at our Division, and there is no need for new acquisitions or financing.

8. Sample size

The sample size was calculated based on a study conducted by Teague et al. (9), which showed that a larger number of women is more comfortable with the presence of a chaperone if the examining physician was a man, compared to the situation in which the examination was conducted by a female physician (31% vs. 14%, $P < 0.01$) (9). Using these differences, with 90% power and 0.05 error was estimated through the SPSS program, it would be required a total of 94 patients in each study group (with or without companion). Considering the volume of first visits attended in our Division of Coloproctology, it is estimated that the data collection will be completed in approximately two years.

9. Statistical Analysis Plan

Categorical variables will be described by absolute and relative frequency (percentage). The quantitative variables with symmetrical distribution will be described by the mean and standard deviation.

Quantitative variables with asymmetric distribution will be described by median and interquartile range (percentiles 25 and 75). Chi-square or Chi-square tests with Yates correction will be used to compare the categorical variables. Quantitative variables with symmetrical distribution will be compared by the Student t test for independent samples. Quantitative variables with asymmetric distribution will be compared by the Mann-Whitney test. A level of statistical significance of 5% shall be considered in all tests used.

10. Cronogram of Activities

Date	Activities
January and February 2018	Elaboration, submission and approval of the research project
July 2018 to July 2020	Data collect
August to September 2020	Statistical analysis
October 2020	Bibliographic review and elaboration of the scientific article

12. References

- 1- The Royal College of Obstetricians and Gynaecologists. Gynaecological examinations, guidelines for specialist practice. London: RCOG, 2002.
- 2- Intimate Examinations. London, UK, General Medical Council. December 2001.
- 3- Gawande A: Naked. *N Engl J Med* 2005, 353(7):645-648.
- 5- College of Physicians and Surgeons of Ontario: Avoid complaints of sexual abuse (policy document) [<http://www.cpso.on.ca/Policies/avoid.htm>].

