There are few studies, however, analyzing the patient's perception of whether or not a chaperone is needed. A study conducted in England attempted to evaluate patients' preference regarding this issue. Questionnaires on the subject were sent to men and women. A total of 190 men and 264 women answered these questionnaires. Of them, 15% were clearly opposed to the presence of companions, while 15% would like a chaperone to be present. The vast majority (59%) replied that they would feel uncomfortable if the chaperone was present without this being authorized by them. Most of the patients that did not want a chaperone considered uncomfortable to have to be exposed to a third person during the examination, which would reduce confidentiality of the consultation and also the trust between doctor and patient (8). A similar study conducted in Australia, also through mail-in questionnaires, showed that more women would be more comfortable with the presence of a chaperone if the examining physician was male compared to the situation in which the physician was a female (31% vs. 14%, P <0.01) (9).

Although the anorectal examination is part of the coloproctological routine, there is no published guideline regarding the need for the presence of a third person during this procedure. In addition, there is no publication so far evaluating the patients' perception of the need and adequacy of the presence of a chaperone during the proctological examination. What is seen in practice is that this decision of having a chaperone varies from doctor to doctor. In our Coloproctology Division, none of the physicians use to have a chaperone during the examination of female patients.

Considering the practical and legal implications of using a chaperone during the routine proctological examination, we propose a prospective study evaluating the perception of female patients regarding this issue.

2. Rationale

Although anorectal examination is part of the coloproctological routine, there is no guidance on the need for chaperone during the examination of female patients. Likewise, there is no study evaluating the patients' perception regarding the use or not of a chaperone during the proctological examination.

3. Objectives

3.1 General Objective:

To evaluate the degree of satisfaction of patients submitted to proctological examination with or without the presence of a chaperone.

3.2 Specific Objectives:

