Correlate the degree of satisfaction of the patients with several clinical-demographic variables, including: age, marital status, diagnosis, comorbidities, symptomatology.

4. Hypotheses

Hypothesis 1: most patients will be satisfied without the presence of a chaperone during the anorectal examination.

Hypothesis 2: Most patients will be dissatisfied without the presence of a chaperone during the anorectal examination.

5. Materials and Methods

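### The objectives and hypotheses are about satisfaction, but section 5.3 makes chaperone preference the main outcome, and comparing preference between arms does not estimate what section 3.1 asks

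*Combined protocol and SAP*

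**What the plan says.** The general objective in section 3.1 is "To evaluate the degree of satisfaction of patients submitted to proctological examination with or without the presence of a chaperone". Section 3.2 keeps the same construct: "Correlate the degree of satisfaction of the patients with several clinical-demographic variables". Section 4 frames both expectations in those terms: "Hypothesis 1: most patients will be satisfied without the presence of a chaperone during the anorectal examination" and "Hypothesis 2: Most patients will be dissatisfied without the presence of a chaperone during the anorectal examination".

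Section 5.3 changes the construct: "The main outcome to be assessed will be patients' preference regarding the presence of a female chaperone during anorectal examination". It then adds, as a further assessment under the same heading, comfort or embarrassment. The questionnaire has six items, each reported alone with no total score. Satisfaction is not defined, and no item asks about it by name.

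On design, section 5.1 says "These patients will be randomized into two groups", with and without a chaperone. Section 9 describes categorical answers by frequencies and compares groups by chi-square, t test or Mann-Whitney. It names no primary item and no test of a majority within one arm.

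**The concern.** Three different quantities are in play, and the plan does not say which one answers the objective:

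- **Satisfaction by chaperone status** (sections 3.1 and 3.2): a contrast between the two randomised conditions.
- **A majority satisfied, or dissatisfied, without a chaperone** (section 4): a proportion under one condition.
- **Preference about a chaperone** (section 5.3): what a woman would choose, asked after the examination.

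Section 9 offers only between-group tests, so the natural analysis of the main outcome is an arm comparison of preference. That comparison matches neither section 3.1 nor section 4. A reader could take a null result as showing that a chaperone makes no difference to satisfaction, or a significant one as showing that it does. Neither follows.

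**Working it through.** **Inputs.** 94 women per group (section 8); item wording from section 5.3 and Annex 2; 5% significance (section 9). The preference splits and the SD of item 1 below are assumptions, because the documents give neither for this population.

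**The plan's own figure.** Section 8 gives 94 per group for 31% against 14%. The usual formula is n = [z(α/2)·√(2p̄(1−p̄)) + z(β)·√(p1(1−p1)+p2(1−p2))]² / (p1−p2)², with p̄ = 0.225.

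- 80% power: (1.960×0.5906 + 0.842×0.5782)² / 0.0289 gives 94.
- The stated 90% power: (1.960×0.5906 + 1.282×0.5782)² / 0.0289 gives 125.

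That discrepancy is a separate matter, so I take 94 as the planned size. What matters here is that the sizing rests on yet another quantity: comfort with a chaperone according to the physician's sex.

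**Step 1: preference on a common coding.** Recode answers to wants / does not want / indifferent. If the examination does not alter preference, randomisation makes the two arms equal in expectation, and a 2×3 chi-square rejects at about its nominal rate (about 5% in simulation at 80% want, 10% oppose). This is so by construction. It shows only that such a test measures the effect of exposure on preference.

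**Step 2: preference as worded.** Item 3 asks the no-chaperone arm whether they would rather have had another woman present (Annex 2). By the alternative wording in section 5.3, it asks the chaperone arm whether they would rather have been without one. So *yes* means *wants a chaperone* in one arm and *does not want one* in the other. Let preference be identical in both arms, with share w wanting and o opposing. Then *yes* is expected from w of one arm and o of the other, and *no* the reverse. With m = (w+o)/2, the chi-square noncentrality is 94 × 4 × [(w−o)/2]² / m on 2 df.

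| Wants / opposes (assumed) | Noncentrality | Simulated rejection, 94 per arm |
|---|---|---|
| 80% / 10% | 376 × 0.35² / 0.45 = 102.4 | 100% |
| 31% / 15% | 376 × 0.08² / 0.23 = 10.5 | about 84% |

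The noncentral approximation for the second row gives 83%. If w = o, the noncentrality is zero and the test rejects at about 5% under either coding. So the result depends on a coding the plan does not state, and neither version is a difference in satisfaction with the examination.

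**Step 3: preference does not determine satisfaction.** With invented counts and a Yates chi-square, preference of 28/94 in both arms gives p = 1.0, while satisfaction of 85/94 against 65/94 gives p = 0.0006. Conversely, preference of 60/94 against 10/94 gives p of about 10⁻¹³ with satisfaction 85/94 in both arms (p = 1.0).

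**Step 4: the hypotheses.** A majority without a chaperone is a one-sample question in 94 women. Excluding 50% takes at least 57/94 (60.6%; exact one-sided p = 0.0247). Power is 49% at a true rate of 60%, 84% at 65% and 98% at 70%. No between-arm test addresses this.

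**Step 5: what the collected data can support.**

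- Item 1, two-sample t test, 94 per arm, two-sided 5%. The normal approximation at 90% power is (1.960+1.282)×√(2/94) = 0.473 SD; allowing for the t distribution it is 0.475 SD. At 80% power it is 0.41 SD. At 90% power, an SD of 2 to 3 gives 0.475×2 = 0.95 to 0.475×3 = 1.43 points.
- Preference in all 188 women: the 95% half-width is 1.96×√(p(1−p)/188), or 5.1 points at 15%, 6.6 at 31% and 7.1 at 50%.

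**The case against.** Much can be said for the plan. Comfort sits under the same primary heading, every item is reported separately, and section 9 already provides frequencies for categorical answers and a t test or Mann-Whitney for the 0 to 10 score. As worded, items 3 and 6 ask whether a woman would switch from, or repeat, the condition she had, which comes close to contentment with it. The items are asked after the examination, so whether the experience shifts preference is a legitimate randomised question. Being satisfied without a chaperone may also simply mean being content with the absence. And item 1 is not satisfaction by name; item 2 is arguably as near.

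This stands against three stronger readings that a reader might infer:

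- *The trial cannot answer its objective.* The documents do not support this: items 1 and 2 are collected and could serve.
- *A null preference comparison carries no information on satisfaction.* That would need preference to be a fixed attitude brought to the visit, which no section states, and a common coding that the plan does not give.
- *The two endpoints give opposite verdicts.* Using the survey in section 1 (15% want a chaperone, 15% are opposed), one could set 85% not wanting one against 15% opposed. These are compatible descriptions of the same answers, and no hypothesis says that most women prefer to be without a chaperone. That survey also mixed 190 men with 264 women, and 59% would be uncomfortable with an unauthorised chaperone, so the remaining 70% cannot be assumed content either way.

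The objection does not remove the mismatch. No section ties any item to satisfaction, and the outcome named as main is a different construct.

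**Conclusion.** The concern holds in this form: the main outcome in section 5.3 does not estimate the contrast in section 3.1, and comparing it between arms does not test either hypothesis in section 4. The mismatch is in the text and rests on no assumption.

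The size of the interpretive problem does rest on assumptions. With identical preference in both arms, a test of item 3 rejects in about 5% of trials on a common coding. As worded it rejects in 100% (80% want, 10% oppose) or about 84% (31%, 15%). Those splits are illustrative, and the divergence vanishes when as many want a chaperone as oppose one.

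This should be corrected but is not fatal, because the questionnaire already contains what is needed.

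**What to change.** Use one set of terms across sections 3, 4, 5.3 and 9:

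1. **Randomised comparison.** Name item 1, the 0 to 10 comfort score, as the endpoint, and state that it stands for satisfaction in sections 3.1 and 3.2. It is already collected and is worded the same way in both arms.
2. **Preference.** State a recoding of items 3 and 6 to wants / does not want / indifferent. Report the shares with 95% confidence intervals (5 to 7 points either side for 188 women). Read any arm difference only as an effect of exposure on preference.
3. **Hypotheses.** Reword both as a proportion of the no-chaperone arm on a named item, and say how *indifferent* counts.

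The cost is wording only: no new data and no extra patients. The real downside is that section 8 would no longer describe the arm comparison. It should instead state the detectable difference for item 1 with 94 per arm: 0.475 SD at the plan's 90% power (0.41 SD at 80%), with a justified SD. The documents give none; 0.95 to 1.43 points at 90% power assumes 2 to 3. If item 2 is thought closer to satisfaction, it could be named instead, but its wording differs between arms and the sizing would have to be redone for a three-category answer.

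### Section 8 borrows a physician-sex difference (31% vs 14%) as the chaperone effect and ties it to no questionnaire item, so the stated 90% power is not established for any planned comparison

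*Combined protocol and SAP*

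**What the plan says.** Section 8 (Sample size) rests on one cited Australian survey. It reports that "a larger number of women is more comfortable with the presence of a chaperone if the examining physician was a man" than if the doctor was a woman, at 31% and 14%. The Introduction describes the same source as a postal survey: "also through mail-in questionnaires, showed that more women would be more comfortable with the presence of a chaperone if the examining physician was male". From that difference, "with 90% power and 0.05 error was estimated through the SPSS program", section 8 concludes that "it would be required a total of 94 patients in each study group (with or without companion").

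Section 5.1 randomises women to examination with or without a chaperone. Physician sex is not an arm, is not among the variables listed in section 3.2, and is not used in section 9.

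On outcomes, section 5.3 says: "The main outcome to be assessed will be patients' preference regarding the presence of a female chaperone during anorectal examination". Comfort is assessed as well. Both are read from six separate items without a total score: one 0-10 scale and five items with three answers. Section 9 plans chi-square tests (with or without Yates correction) for categorical variables, and the t-test or Mann-Whitney test for quantitative ones. It adds: "A level of statistical significance of 5% shall be considered in all tests used".

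**The concern.** The two rates describe women's views about having a chaperone under two physician sexes. The trial compares two examination conditions. Nothing in the plan says why the first difference should equal the second, or why 17 points would be a relevant difference between the arms. The rates are also attached to no item. No three-answer item is reduced to two categories, and no expected rate is given for either arm.

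Items 3 and 6 add a difficulty. Section 5.3 words them in opposite directions in the two arms, and Annex 2 confirms the no-chaperone wording. In item 3, a yes in the chaperone arm means the woman would rather have had no third person; in the other arm it means she would rather have had one. A two-proportion calculation cannot be applied to such an item until a common definition of response is set.

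What is at stake is how the results are read. A null comparison could be reported as coming from a trial with 90% power for a relevant effect, although no chaperone effect was specified. The main outcome, preference, would be reported with no precision planned for it.

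**Working it through.** **Inputs.** From section 8: p1 = 0.31, p2 = 0.14, error 0.05, power 90%, 94 per group. Sidedness is not stated; two-sided is taken and one-sided is also tried.

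**1. The plan's own figure.** For two proportions (normal approximation, pooled variance under the null, equal groups):

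n = [z(α)·√(2·p̄·(1−p̄)) + z(β)·√(p1(1−p1) + p2(1−p2))]² / (p1−p2)²

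- p̄ = (0.31 + 0.14)/2 = 0.225; √(2 × 0.225 × 0.775) = 0.5906; √(0.2139 + 0.1204) = 0.5782.
- 90% power: (1.96 × 0.5906 + 1.2816 × 0.5782)² / 0.17² = (1.1575 + 0.7410)² / 0.0289 = 124.7, so 125 per group.
- 80% power: (1.1575 + 0.8416 × 0.5782)² / 0.0289 = (1.1575 + 0.4866)² / 0.0289 = 93.5, so 94 per group.

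The stated 94 is reproduced at 80% power, not at 90%. A one-sided test at 90% needs 102. With continuity correction, 90% power needs 137 (two-sided) or 113 (one-sided).

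Power at 94 per group: z = (0.17 × √94 − 1.1575)/0.5782 = (1.6482 − 1.1575)/0.5782 = 0.849, which gives 80.2%. By exact enumeration it is 80.9% for the chi-square test and 76.2% with Yates correction. One-sided power is 87.9%.

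**2. The same 17-point gap at other base rates.** The documents give no rates for chaperone vs no chaperone, so these bases are assumptions (94 per group, two-sided 5%, same formula):

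| Assumed rates | Power |
|---|---|
| 22% vs 5% | 93% |
| 27% vs 10% | 86% |
| 31% vs 14% (section 8) | 80% |
| 40% vs 23% | 71% |
| 50% vs 33% | 66% |
| 58.5% vs 41.5% | 65% |

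**3. What 94 per group gives for preference.** The 95% CI half-width is 1.96·√(p(1−p)/n).

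- Per arm (n = 94): 7.2 points at p = 0.15 and 10.1 points at p = 0.50.
- Both arms (n = 188): 5.1 and 7.1 points. This has a meaning only after the mirrored items are recoded to one direction.
- Between arms, from a 50% base, the detectable difference at 80% power is 19.9 points (50% vs 69.9%).

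**4. What 94 per group gives for item 1 (0-10 comfort).** Solving the two-sample t-test at n = 94 per group gives a detectable difference of 0.411 SD at 80% power and 0.475 SD at 90%. The SD is not given. If it is 2 to 3 points (assumption), this is 0.8 to 1.2 points at 80% power and about 1.0 to 1.4 points at 90%.

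**The case against.** The Introduction and section 2 state that no study has addressed patients' perception of a chaperone at proctological examination. Some surrogate was therefore needed, and the borrowed quantity, women's comfort with a chaperone, lies in the same field as the outcomes in section 5.3. Section 8 assigns the number to the trial's own two arms, and section 9 plans chi-square tests. The share choosing a given answer to items 2-6 is a proportion, so a two-proportion calculation could fit an item reduced to two categories.

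All of that stands, and it limits the point. A reader might infer that the power figure relates to no comparison in the plan, or that a correct calculation at 31% vs 14% would tell us nothing. The documents do not support that. The comparison is named, and such a calculation shows what gap two arms of 94 can detect if an item has those rates. Nor does the borrowed contrast by itself make the power low: at lower base rates the same gap has more than 80% power. The fall from 90% to 80% at 31% vs 14% comes from the arithmetic, not from the choice of contrast.

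It can also be said that the hypotheses in section 4 ask what most patients feel without a chaperone, which is a question of estimation more than of power. That is fair, and it is a reason to state precision, which section 8 does not do.

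None of this supplies the missing link: why a difference by physician sex should serve as the chaperone effect, on which item, and with which definition of response.

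**Conclusion.** The point holds in a limited form. The inputs to section 8 are an unjustified surrogate tied to no item or response definition, so 90% power is not established for any planned comparison. Even on its own inputs the figure is about 80%. Across the assumed base rates, power for a 17-point gap runs from about 93% to 65%. The documents do not say where in that range the trial lies.

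It does not follow that 94 per arm is too small, or that another number is right. With no expected rates for chaperone vs no chaperone, no corrected sample size can be derived. Raising the number to 125 would mend the arithmetic and leave the borrowed contrast in place.

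The results assume a two-sided 5% test, equal groups, and 94 analysed women per arm. The figures for item 1 assume a t-test and are approximate if Mann-Whitney is used, as section 9 allows for asymmetric data.

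**What to change.** Keep 94 per arm, remove the claim of 90% power based on 31% vs 14%, and restate in section 8 what 94 delivers for the trial's own outcomes:

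- **Preference (main outcome).** Name the item. Recode the mirrored wording to one direction, for example to whether the woman would prefer a chaperone, and say how the indifferent answer is counted. Then give the 95% CI half-width (at worst about 10 points per arm, and about 7 points pooled after recoding) and the detectable difference between arms (about 20 points from a 50% base at 80% power).
- **Item 1 comfort (also assessed).** Give the detectable difference of about 0.41 SD at 80% power or 0.48 SD at 90%, with the assumed SD. Say that it rests on a t-test and is approximate under Mann-Whitney.

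This costs a rewording of section 8 and a short recoding rule, with no extra patients and no change to randomisation or data collection. The stated figure will be less favourable than 90% power. Section 8 will also still lack a justified chaperone effect: it will report what 94 per arm can show, without claiming that this is the difference that matters.
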